### 6.1.4 Sample Size Re-estimation

There are no planned sample size re-estimations.

## 6.2 Adjustments for Covariates

It is planned that all statistical analyses will be stratified by geographical region (US/Non-US) and primary tumor location (GB/non-GB), in accordance with the stratification factors declared at randomization.

### 6.3 Handling of Dropouts or Missing Data

In general, missing data will remain missing and will not be included in analyses. Exceptions are described below.

- **Missing Baseline Data**

If a baseline (Day 1) value is not available and a screening value is available for the same parameter, then the last screening value will be used as baseline. This value will also be used for calculations of changes from baseline.

- **Missing % Change from Baseline in Sum of Longest Diameters of Target Lesions (TLs) at Week 12**

An increase from baseline of 20% will be imputed for any subjects who die by any cause, or withdraw from the study due to symptomatic disease progression prior to Week 12+ 5 days. Any subjects who withdraw from the study due to radiological disease progression prior to Week 12 will be included in the analysis, and will be assigned a percentage change from baseline of 20%, or the value that was observed at the time of disease progression (whichever is larger).

- **Missing Best % Change from Baseline in Sum of Longest Diameters of TLs at any time**

For the waterfall plot of the best % change from baseline, subjects with measurable disease at baseline (see Section 4.3), for whom no post-baseline TL data are available, will have an increase from baseline of 20% imputed in the following circumstances:

- The subject has died prior to week 12 (+ 5 days)
- Progression has been detected based on NTLs or new lesions prior to week 12 (+ 5 days)
- Subject has withdrawn due to symptomatic progression prior to week 12 (+ 5 days)

### 6.4 Monitoring and Interim Analyses

#### 6.4.1 Monitoring

The study will be monitored to ensure that the study is conducted and documented properly according to the protocol, good clinical practice (GCP), and all applicable regulatory requirements.

#### 6.4.2 Interim Analysis

Data from the open-label Safety lead-in will be reviewed on an ongoing basis, and a Data Safety Monitoring Board (DSMB) meeting will occur once the first 12 subjects have completed one cycle of treatment (with a minimum 85% compliance over the first 14 days). The purpose of the initial DSMB meeting is to review the safety and tolerability data prior to commencement of Part 1 of the study.

There are no interim analyses planned during Part 1 or 2. The primary analysis of Part 1 will be the later of 3 months after Last Subject In (LSI) or when 70% of the subjects (84 subjects) have experienced a PFS event. At this time, a database lock will be performed and the primary analysis of all primary and secondary endpoints will be performed. The data cut-off for Part 2 will be following the 247th OS event. Whilst Part 2 is ongoing, further efficacy and safety data may continue to be accrued for Part 1 subjects. For example, further OS events occurring after the primary analysis of Part 1 will continue to be collected and databased.

The database for both parts of the study will be locked at the data cut-off for the Part 2 analyses.

Data for any subjects who continue to receive treatment beyond this point will be reported as a further addendum to the CSR.

## 6.5 Multiple Testing Strategy

### 6.5.1 Part 1

Part 1 is designed with co-primary endpoints, ORR and PFS. In order to maintain an overall, one-sided 10% type I error rate for Part 1, a **Hochberg** procedure will be used, such that the trial will be deemed to have met its primary objective if either endpoint is significant at the one-sided 5% level, or if both endpoints are significant at the one-sided 10% significance level. If the trial meets its primary objective as described above, all secondary efficacy endpoints will also be tested at the one-sided 10% significance level to better understand the clinical benefit offered by varlitinib treatment.

Furthermore, if the primary objective of the study is met, as described above, statistical significance at the two-sided 5% level will be tested to support marketing approval. For this assessment, the following approach to type I error control will be applied:

- The overall type I error rate for marketing approval will be controlled at the two-sided 5% level, using a Hochberg procedure
- Using this approach, statistical significance may be claimed if *either* ORR or PFS is significant at the two-sided 2.5% significance level or if *both* ORR and PFS are significant at the two-sided 5% significance level.

If statistical significance is demonstrated using the approach described above, the secondary endpoints OS and DCR will also be assessed at the two-sided 5% significance level, in order to further describe the nature of the benefits offered by varlitinib treatment, to support marketing authorisation.

For the purpose of supporting marketing approval, all hypothesis testing at significance levels higher than 5% will be considered exploratory.

### 6.5.2 Part 2

In order to describe the nature of the benefits of varlitinib treatment, OS, ORR, PFS and DCR will all be tested at a 2-sided significance level of 5%.

However, in order to strongly control the type I error at the two-sided 5% level, the following hierarchical testing order is defined for the Part 2 efficacy endpoints: OS – ORR – PFS – DCR.

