Overall Survival is a secondary endpoint in Part 1. A preliminary analysis of OS will be performed at the time of the primary analysis of ORR and PFS. It is anticipated that the OS data at this time will be immature, thus a second analysis of OS is planned for when approximately 95 patients (approx. 79%) have an OS event. Due to the number of OS events expected at the time of the first analysis, this initial analysis of OS will be considered exploratory only. Although a p-value may be presented, for the purpose of marketing authorization, no claims of statistical significance will be based on the initial analysis. For the purpose of type I error control across the two analyses of OS in support of marketing authorization, the OS update analysis will be considered the primary analysis of OS for Part 1 of the study, and statistical significance will be assessed at the two-sided 5% significance level.

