### 3.1.5 Disease Control Rate

DCR rate is defined as the number (%) of subjects with at least one visit response of CR or PR, or with stable disease for a minimum of twelve weeks (-5 days) from randomization. Data obtained up until progression, or last evaluable assessment in the absence of progression, will be included in the assessment of DCR. This will be irrespective of whether or not subjects discontinued treatment or received a subsequent therapy prior to progression. For all study parts, the primary assessment of DCR will be based on the FAS. For Part 1, DCR will be calculated based on data from the ICR. For Part 2 and the Safety lead-in, DCR will be calculated from the site radiological data.

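### Part 1's two-sided 5% control for marketing covers only ORR and PFS, yet a single primary win also opens OS at a full 5% in support of marketing

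*SAP*

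**What the plan says.** SAP 6.5.1 (Multiple Testing Strategy, Part 1) makes this statement: "The overall type I error rate for marketing approval will be controlled at the two-sided 5% level, using a Hochberg procedure". The rule that follows names only ORR and PFS. A claim is allowed if either is significant at two-sided 2.5%, or both at two-sided 5%.

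If that succeeds, "the secondary endpoints OS and DCR will also be assessed at the two-sided 5% significance level", and the stated purpose is "in order to further describe the nature of the benefits offered by varlitinib treatment, to support marketing authorisation". No order, split or carry-over of error is given for the two secondaries. The section closes by saying that, for marketing approval, "all hypothesis testing at significance levels higher than 5% will be considered exploratory". OS and DCR are tested at exactly 5%, so that label does not reach them.

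Protocol 8.2.2 treats Part 1 OS in the same way and mentions no gate. It opens with "For the purpose of type I error control across the two analyses of OS in support of marketing authorization", names the later OS analysis as primary, and says that "statistical significance will be assessed at the two-sided 5% significance level".

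For Part 2, SAP 6.5.2 takes a different course: "in order to strongly control the type I error at the two-sided 5% level, the following hierarchical testing order is defined". Part 1 has no counterpart for its secondaries.

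**The concern.** Hochberg protects the ORR–PFS pair. It does not protect a larger set of claims that one win in the pair unlocks. After a win on one primary at 2.5%, the other primary can still be rejected at up to 5%, and OS receives a fresh 5% of its own. If the other primary and OS are both truly null, two null hypotheses are each being tested at 5%.

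The consequence would be a marketing package that reports a false PFS or OS benefit more often than the 2.5% per direction that a two-sided 5% rule implies. The main case is a drug that shrinks tumours without delaying progression or death, where a mistaken time-to-event claim would mislead most.

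**Working it through.** **Inputs.** ORR 10% vs 30% with 120 patients (60 per arm), 84 PFS events with HR 0.54, and control median PFS 2.67 months (protocol 8.2.2, SAP 6.1.2). About 95 events for the Part 1 OS update (protocol 8.2.2). OS HR 0.7 is the Part 2 planning value, used only for the cost of the alternative fix. Correlations between endpoints are assumptions. ORR is tested by unstratified Fisher's exact test with the one-sided p doubled; the plan's test is stratified.

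**The plan's own figures.**
- Hochberg on two independent nulls: 0.05² + 2 × 0.025 × 0.95 = 0.0025 + 0.0475 = 5.0%, as stated.
- PFS power: −ln(0.54) × √84 / 2 = 2.82; Φ(2.82 − 1.96) = 80.6%, as stated.
- ORR power: 78.9% by normal approximation, close to the stated 80%; about 73% by Fisher's exact test.

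**Only response effective; PFS and OS null; all tests independent.** Fisher power is about 73% at two-sided 5% and about 63% at 2.5%.
- False PFS claim: 0.025 + 0.025 × 0.73 = 4.3%.
- OS claim without a PFS claim: ORR wins at 2.5%, PFS p exceeds 5%, OS p is at most 5%: 0.63 × 0.95 × 0.05 = 3.0%.
- Total: 4.3% + 3.0% = 7.3% two-sided.

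Simulation (1,000,000 trials per scenario; PFS and OS z-scores bivariate normal with mean shift −ln(HR) × √events / 2) agrees: 7.3–7.4% in repeat runs at zero correlation, with the gate open in 64% of trials.

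| Truth | False claim counted | Two-sided | Benefit direction |
|---|---|---|---|
| Only ORR effective; ORR independent, PFS–OS correlation 0.7 to 0 | PFS or OS | 6.4–7.3% | 3.2–3.7% |
| Only ORR effective; ORR also correlated with PFS and OS, up to 0.5 | PFS or OS | about 6.0–7.2% | about 4.4% with all three correlations at 0.5 |
| Only PFS effective, HR 0.54; ORR independent | ORR or OS | 4.6–5.5% | 2.8–3.5% |
| Both primaries at planned effects, OS null; ORR independent | OS | 4.1–4.5% | 2.3–2.5% |
| Nothing effective; ORR independent | any of ORR, PFS, OS | about 3.6% | not tabulated |

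The fourth row can be checked by hand at zero correlation: the gate opens in 90.5% of trials, and 0.905 × 5% = 4.5%. OS taken alone cannot exceed 5%, because the gate can only remove rejections.

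**Why no figure is given for DCR.** SAP 3.1.5 counts patients "with at least one visit response of CR or PR, or with stable disease for a minimum of twelve weeks (-5 days) from randomization", so every responder is a DCR success. A real PFS effect also moves DCR. With exponential PFS, day 84 is 2.76 months, so control 12-week PFS is 0.5^(2.76/2.67) = 48.8%, against 0.488^0.54 = 67.9% on varlitinib. At day 79 the figures are 51.0% and 69.5%. A null DCR beside an effective ORR or PFS is hardly attainable.

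**The case against.** **Scope.** Part 1 never promises strong control. Its Hochberg bullets name ORR and PFS, that pair is controlled as stated, and the secondaries are gated and said to describe benefit further. Much of this stands: a reader might infer that the SAP breaks an explicit strong-control promise, and it does not, because that wording appears only for Part 2. The purely descriptive reading still fails. The tests are meant to support authorisation, only tests above 5% are called exploratory, and protocol 8.2.2 assesses OS significance at 5% for marketing.

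**Plausibility.** A 20-point response gain with exactly null PFS is a strained scenario, since both endpoints come from the same central review. That is fair, and it is why the excess is called modest. The design plans effects on both primaries, and there the rule holds. But response without PFS benefit is not excluded by definition, as a null DCR nearly is, and the plan allows a marketing claim on ORR alone.

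**Size.** The excess depends on correlation. At PFS–OS correlations of 0.8 and 0.9 the response-only error falls to 6.1% and 5.6% (benefit 3.0% and 2.8%). In the PFS-only case the two-sided error is at or below 5% from a correlation of 0.5 upward. Both points stand.

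**Larger figures a reader might infer.** Counting OS and DCR as two equal leaks gives 1 − 0.95² = 9.75%. Adding a null second primary gives 1 − 0.95³ = 14.3%. Both need a null DCR beside a strongly effective primary, which the DCR definition makes hardly attainable. Without DCR, 9.75% is also the ceiling for a null second primary plus null OS. It needs independent tests and a gate that opens in every trial, whereas at the planned response effect it opens in 64%.

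**Conclusion.** The point holds, at modest size. The Part 1 rule controls error for ORR and PFS and when nothing works, but not for the whole set of claims it offers for marketing. The leak is OS opening at a full 5% after a single primary win.

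The clearest excess is in the response-only case: about 6.4–7.3% two-sided and 3.2–3.7% for benefit with ORR independent, and about 4.4% for benefit with all three correlations at 0.5. With only PFS effective, the two-sided error barely passes 5%, while the benefit-direction error is 2.8–3.5%. The absence of a rule is certain from the text. The sizes rest on assumed correlations and an unstratified test of ORR.

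A reader might also infer that analysing Part 1 OS twice adds error. It does not: protocol 8.2.2 and 8.5.2.1 bar significance claims at the first analysis.

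**What to change.** **Preferred.** State in SAP 6.5.1 and protocol 8.2.2 and 8.5.2.1 that the two-sided 5% control covers ORR and PFS only. State also that Part 1 OS and DCR are supportive, reported with nominal p-values and confidence intervals and no formal significance claim. This is wording only. The cost is no formal OS or DCR claim from Part 1; OS is tested as the primary endpoint of Part 2.

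**Alternative, if formal claims are wanted.** Test OS, then DCR, in fixed sequence at two-sided 5%, only when Hochberg rejects both ORR and PFS. In the response-only case a false OS claim then requires a false PFS claim, so the error falls back to the PFS part, about 4.3% two-sided (2.1–2.2% for benefit, ORR independent). Ordering OS before DCR while one win still opens the gate would not close the leak.

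The alternative costs power. With OS HR 0.7 and 95 events, −ln(0.7) × √95 / 2 = 1.74, so power is Φ(1.74 − 1.96) = 41%. At planned effects with ORR independent, at least one primary wins in 90.5% of trials and both in 58.9%. With independent tests, formal OS claims fall from 0.905 × 41.2% = 37% to 0.589 × 41.2% = 24%. Over PFS–OS correlations 0 to 0.7 the fall is from 37–40% to 24–29%. If ORR correlates with PFS and OS, it is from about 39–40% to 32%. A DCR claim would also have to wait for OS.

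**Separate alignment point, which adds no error.** SAP 6.4.2 and 7.3 place Part 1 OS at the ORR/PFS cut-off. They should place any OS significance test at the update at about 95 events, as protocol 8.2.2 and 8.5.2.1 state.

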## 6.6 Examination of Subgroups

For ORR (Part 1), PFS (Part 1) and OS (Part 2), sub-group analyses will be performed to investigate the consistency of the treatment effect across expected prognostic factors, and possible predictive factors. The sub-groups to be explored are the stratification factors region (US/Non-US) and primary tumor location (GB/Non-GB), plus the following factors:

- Gender (Male vs. Female)
- Race (Asian/Caucasian/Other)
- Baseline ECOG Status
- Extent of Disease (Locally Advanced/Metastatic)
- Age (<60/>=60)
- Baseline HER2 expression (positive defined as +++ or above by IHC, otherwise negative)
- Any HER positivity (positive defined as + or higher by IHC for HER1, HER2, HER3 or HER4, otherwise negative)

These sub-group analyses will be performed using the primary analysis population, and considered supportive of the primary analyses, thus no adjustment to the significance level will be made.

Sub-group analyses will not routinely be performed for the sensitivity analysis populations, unless the main sensitivity analysis results do not concur with the primary analysis, and further investigation is required.

## 6.7 Stratification Factors

As described in Section 2.2, for Parts 1 and 2, the randomization scheme will be stratified by region (US/Non-US) and primary tumor location (GB/Non-GB). It is planned that all formal statistical analyses will be stratified by the same two factors, using the values declared at randomization.

In the event that any individual stratum is very small, and contains limited information (i.e. events or responders), certain stratified analysis techniques may result in the entire stratum's data being "omitted" from the fitted model. Furthermore, even when the primary analysis can be fitted, if the information within the stratum is limited, the treatment by stratum interaction tests are unlikely to be meaningful, and the planned sub-group analyses may also become problematic.

If there are fewer than 8 patients in any of the 4 strata, the number of events (PFS and OS) and responders (ORR and DCR) within the affected stratum will be reviewed, prior to study unblinding. If at the blind review stage there is deemed to be insufficient information within the stratum to make the planned stratified analysis meaningful, geographical region will be "dropped" as a stratification factor from the statistical analyses, and the primary analyses would remain stratified by primary tumor location (GB/non-GB). The reason for removing geographical region rather than primary tumor

location as a stratification factor, is that it is anticipated that the percentage of GB:non-GB patients will be closer to 50:50, therefore geographical region is the stratification factor most likely to be driving the small stratum.

In this scenario, geographical location (US/non-US) would be added to the list of factors to be explored as part of the planned sub-group analyses. As noted above, any decision to exclude geographical region as a stratification factor in the analysis would be made prior to study unblinding, and would be fully documented in the study file.

## 7. Methods of Analysis

### 7.1 Objective Response Rate

All RECIST-based data will be listed, and the BoR and ORR will be summarized by treatment group. For those subjects with a BOR of PD, the summary will include sub-categories to distinguish between PD as defined by the RECIST criteria, and early deaths that have been assigned to the PD category (see Section 3.1.1). A listing of early deaths will also be provided.

As described in Section 3.1.1, and in accordance with RECIST v1.1, response confirmation is not required in order for a subject to be classified as a responder for the assessment of ORR. For Part 1 only, descriptive statistics will also be produced for BoR and ORR, based on confirmed responses only using the FAS set. For this summary table, to be classified as a responder, the subject would need to have at least two assessments where the visit response is PR or CR, without any intermediate assessments indicative of progression.

There will be no formal analyses of efficacy data from the Safety lead-in. For Parts 1 and 2, the primary analysis will test for the superiority of varlitinib-containing treatment arm relative to the placebo-containing arm.

Objective Response Rate will be analyzed using a stratified exact binomial test (Mehta et al, Emerson) which extends Fisher's Exact test to more than one strata. The analysis will be stratified by region (US/Non-US) and primary tumor location (Gall Bladder/Non-GB). The 2-sided p-value will be obtained by doubling the 1-sided p-values.

The conditional maximum likelihood estimate of the odds ratio will be presented together with its exact 2-sided 95% confidence limit, which excludes one if and only if the stratified exact binomial test is significant at a 2-sided 5% level. For Part 1 only, corresponding significance levels and confidence intervals will be calculated using tests performed at a 1-sided 10% level. The one-sided P-value will also be presented.

To test for heterogeneity across strata, the exact test of Zelen will be performed by testing whether the treatment effect differs between the 4 strata included in the primary analysis.

For Part 1 only, subgroup analyses will be conducted comparing ORR between treatments in the subgroups of the FAS set defined by the stratification factors Region (US/Non-US) and primary tumor location (GB/Non-GB), plus the following factors:

- Gender (Male vs. Female)
- Race (Asian/Caucasian/Other)
- Baseline ECOG Status
- Extent of Disease (Locally Advanced/Metastatic)
- Age (<60/>=60)
- Baseline HER2 expression (positive defined as +++ or above by IHC, otherwise negative)
- Any HER positivity (positive defined as + or higher by IHC for HER1, HER2, HER3 or HER4, otherwise negative)

Other baseline variables may also be included if there is clinical justification or an imbalance is observed across the treatment arms.

For Part 1, for each sub-group, the odds ratio and corresponding 80% confidence interval will be presented on a forest plot including the odds ratio and 80% CI from the overall population. Additionally, if the primary analysis of ORR is significant at the two-sided 5% level in the overall population, the forest plot will be replicated using 95% confidence intervals.

No adjustment to the significance level for testing will be made since all these analyses will be considered supportive of the primary analysis of ORR.

Subjects whose data contributed to the Part 1 analysis will not contribute to the Part 2 analysis.

For Part 1, the primary analysis of ORR based on ICR will be performed using the FAS set, and two sensitivity analyses will be performed using the EFR and PP sets. Note that the subgroup analyses will not be repeated for the sensitivity analyses. ORR based on site assessments is a secondary endpoint and will be analyzed using the FAS set. No sub-group analyses are planned for this secondary endpoint.

For Part 2, the primary analysis of ORR will be performed using the FAS set, based on the site assessments of radiological data. No subgroup analyses are planned for ORR in Part 2.

## 7.2 Progression-Free Survival

In Parts 1 and 2, the primary analysis will test for the superiority of the varlitinib-containing treatment arm relative to the placebo-containing arm, as assessed by PFS.

In Part 1, the data cut-off for the primary analysis of PFS will be the later of 12 weeks after LSI and 84th documented PFS event. The primary analysis of PFS will be based on data from the ICR. An analysis of PFS based on site assessments will be used to assess the sensitivity of the primary analysis to informative censoring. See Section 7.2.1.2.

In Part 2, PFS will be analyzed at the time of the primary analysis of OS. The Part 2 PFS analysis will be based on the site assessments of radiological data.

In both study parts, PFS will be analyzed using a stratified log-rank test using the Breslow method to handle ties (Breslow, 1974). The stratification factors are

geographical region (US/Non-US) and primary tumor location (GB/Non-GB). The results will be presented in terms of the HR (with a HR <1 favoring the varlitinib-containing arm) and associated two-sided 95% confidence interval (CI) and two-sided p-value. For Part 1 only, the 80% confidence interval and one-sided p-value will also be presented. The HR and its CI can be estimated from the log-rank as follows (Berry et al 1991, Collett, 2003, Sellke and Siegmund 1983):

$$HR = \exp(U/V)$$

$$95\% \text{ CI for HR} = (\exp\{U/V - 1.96/\sqrt{V}\}, \exp\{U/V + 1.96/\sqrt{V}\})$$

Where  $U = \sum_k U_k = \sum_k \sum_i (d_{1ki} - e_{1ki})$  is the stratified log-rank test statistic obtained from the SAS LIFETEST procedure,  $\sqrt{V} = \sqrt{\sum_k V_k}$ , is its standard deviation,  $k$  denotes the stratum and  $d_{1ki}$  and  $e_{1ki}$  are the observed and expected events in group 1, stratum  $k$ .

Kaplan-Meier (KM) plots of PFS, with tick marks to identify censored observations, will be presented by treatment group. Summaries of the number and percentage of subjects experiencing a PFS event, and the type of event (RECIST 1.1 progression or death) will be provided along with median PFS for each treatment.

The assumption of proportionality will be assessed.

For Part 1 only, subgroup analyses will be conducted comparing PFS between treatments in the subgroups of the full analysis set defined by the stratification factors Region (US/Non-US) and primary tumor location (GB/Non-GB), plus the following factors:

- Gender (Male vs. Female)
- Race (Asian/Caucasian/Other)
- Baseline ECOG Status
- Extent of Disease (Locally Advanced/Metastatic)
- Age (<60/>=60)
- Baseline HER2 expression (positive defined as +++ or above by IHC, otherwise negative)
- Any HER positivity (positive defined as + or higher by IHC for HER1, HER2, HER3 or HER4, otherwise negative)

Other baseline variables may also be assessed if there is clinical justification. For each subgroup, the HRs (varlitinib: placebo) and associated CIs will be calculated from a log rank test within each individual subgroup. These will be presented on a forest plot including the HR and 80% CI from the overall population. Additionally, if the primary analysis of PFS is significant at the two-sided 5% level in the FAS, the forest plot will be replicated using 95% confidence intervals.

The purpose of the subgroup analyses is to assess the consistency of treatment effect across expected and possible prognostic and predictive factors. No adjustment to the significance level for testing will be made since all these analyses will be considered supportive of the primary analysis of PFS.

For both Part 1 and Part 2, Cox proportional hazards modeling will be employed to assess the effect of covariates on the HR estimate. Before embarking on more detailed modeling, an initial model will be constructed, containing treatment and the two stratification factors alone, to ensure any output from the Cox modeling is likely to be consistent with the results of the stratified log-rank test.

The presence of quantitative interactions will be assessed formally by means of an overall global interaction test. This will be performed in the full analysis set by comparing the fit of a Cox proportional hazards model including treatment, all covariates, and all covariate-by-treatment interaction terms, with one that excludes the interaction terms and will be assessed at the 2-sided 10% significance level. If the fit of the model is not significantly improved then it will be concluded that overall the treatment effect is consistent across the subgroups.

If the global interaction test is found to be statistically significant, an attempt to determine the cause and type of interaction will be made. Stepwise backwards selection will be performed on the saturated model, whereby (using a 10% 2-sided level throughout) the least significant interaction terms are removed one-by-one and any newly significant interactions re-included until a final model is reached where all included interactions are significant and all excluded interactions are non-significant. Throughout this process all main effects will be included in the model regardless of whether the corresponding interaction term is still present. This approach will identify the factors that independently alter the treatment effect and prevent identification of multiple correlated interactions.

Any quantitative interactions identified using this procedure will then be tested to rule out any qualitative interaction using the approach of Gail and Simon 1985.

For both parts, the primary analysis of PFS will be based on the programmatically derived PFS using all scans regardless of whether they were scheduled or not.

The primary analysis will be performed on the FAS.

Subjects whose data contributed to the Part 1 analysis will not also contribute to the Part 2 analysis.

